2. AIMS AND OBJECTIVES

PICCOLO has two separate clinical objectives. These are:

Objective 1 (irinotecan modulation with ciclosporin): to establish whether the toxicity of irinotecan therapy is reduced, without loss of efficacy, by modulation with ciclosporin

Objective 2 (addition of panitumumab): to establish whether, in patients with *K-RAS* wild-type tumours, the efficacy of irinotecan therapy is improved by the addition of panitumumab

To address these objectives, the trial poses specific questions using primary and secondary endpoints, fully described in section 10. The general approach is:

Objective 1 (comparison: Ir versus IrCs).

- A sensitive primary outcome measure – proportion of patients alive without evidence of disease progression 12 weeks after randomisation – is used to establish non-inferior anti-cancer efficacy for the **IrCs** combination
- Provided this non-inferiority condition is satisfied, secondary outcome measures will be used to determine whether **IrCs** has improved tolerability (reduced diarrhoea; reduced overall toxicity; improved patient acceptability and/or improved quality of life). In addition, overall survival will be used as a secondary outcome measure to confirm non-inferiority.

Objective 2 (comparison: Ir versus IrPan).

- A robust primary outcome measure – overall survival – is used to establish whether, in patients with *K-RAS* wild-type tumours not previously treated with anti-EGFr therapy, **IrPan** has superior efficacy to Ir.
- Secondary outcome measures will be used to compare the toxicity, patient acceptability and quality of life associated with the two regimens in patients not previously treated with anti-EGFr therapy. Secondary anti-cancer efficacy measures of disease response and progression will also be applied to assess superiority of IrPan in these patients.
- A small proportion of patients will have received a prior anti-EGFR targeted therapy. They will be considered in a separate exploratory comparison of efficacy using a sensitive outcome measure (proportion of patients progression-free at 12 weeks) to address the question whether panitumumab enhances irinotecan sensitivity in this context and to also assess toxicity. This exploratory analysis will consider only those patients with wild-type *K-RAS* status who have previously received an anti-EGFR targeted therapy.

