3. TRIAL DESIGN

PICCOLO is a multi-centre, open-label, randomised, controlled, 4 arm clinical trial designed to show whether, regardless of tumour subtype, the novel regimen **IrCs**, is non-inferior for anti-cancer efficacy and superior for toxicity compared to **Ir**, and whether, in patients with *K-RAS* wild-type tumours, the addition of panitumumab to irinotecan, **IrPan**, gives superior anti-cancer efficacy compared to **Ir** alone.

Potential PICCOLO patients are invited to consent to retrieval of stored tumour samples to test for *K-RAS* mutations at codons 12, 13 and 61. Thereafter, patients who fulfil the eligibility criteria and give informed consent are randomised according to their tumour *K-RAS* status as shown in the flow diagram on page 5.

Patients whose tumours are shown to have a mutation in *K-RAS*, and those in whom *K-RAS* genotyping is not possible due to assay failure or unavailability of tissue, are allocated on a 1:1 random basis to receive **Ir** or **IrCs**. This randomisation uses the minimisation factors listed in the flow diagram.

Patients whose tumours are wild-type for *K-RAS* are allocated on a 1:1 random basis to receive **Ir** or **IrPan**. This randomisation is stratified according to whether or not the patient has received prior anti-EGFR targeted therapy (e.g. cetuximab or panitumumab), and uses the minimisation factors listed in the flow diagram.

Recruitment to PICCOLO will continue until 480 non-EGFR-pre-treated *K-RAS* wild-type patients have entered the **Ir** vs. **IrPan** randomisation (240 patients per arm), and 750 patients have entered the **Ir** vs. **IrCs** randomisation (375 patients per arm). The **Ir** vs. **IrPan** comparison includes approximately 143 patients fulfilling these criteria who were randomly allocated to **Ir** or **IrPan** under Protocol Version 1 (in whom *K-RAS* status is being determined retrospectively), plus approximately 337 patients to be recruited using Protocol Version 2. The **Ir** vs. **IrCs** comparison includes 329 patients randomly allocated to **Ir** or **IrCs** under Protocol Version 1 (regardless of their *K-RAS* status), plus approximately 421 patients to be recruited using Protocol Version 2. The recruitment ratio to the **Ir** vs. **IrCs** comparison and the **Ir** vs. **IrPan** comparison is dependent upon the proportion of patients with unknown *K-RAS* status (which we

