10.2 Secondary Endpoints

Ir vs IrCs comparison

- Proportion of patients free from treatment failure at 12 weeks
- Overall survival (OS) from randomisation
- Research nurse-assessed toxicity (NCI-CTC[V3] grades): maximum toxicity grade per patient; rate per cycle; all-cause mortality within 60 days of randomisation; toxicity of primary interest is grade 3+ diarrhoea within 12 weeks of randomisation;

Ir vs IrPan comparison (patients with wild-type K-RAS status not previously receiving an anti-EGFR targeted therapy)

- Proportion of patients progression-free 12 weeks from randomisation.
- Research nurse-assessed toxicity (NCI-CTC[V3] grades): maximum toxicity grade per patient; rate per cycle; all-cause mortality within 60 days of randomisation;

Ir vs IrCs and Ir vs IrPan (patients with wild-type K-RAS status not previously receiving an anti-EGFR targeted therapy) comparisons

- Progression-free survival (PFS) from randomisation
- Best response by RECIST criteria within 1-year follow-up from randomisation
- Patient-assessed symptom/QL/PA scores at 12 and 24 weeks

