Analysis of 12-week assessments will include all patients assessed between 10 and 14 weeks from randomisation. A sensitivity analysis will be conducted to allow for patients assessed outside of this 2 week time frame. Analysis of response will be performed using the centrally reviewed outcome. If the centrally reviewed outcome is missing, the primary analysis will class the patient as being progression-free at 12 weeks (if alive), and a sensitivity analysis will be conducted using the outcome of the local assessment. If this is also missing, the patient will be classed as having progressed at 12 weeks in the sensitivity analysis.

A two-sided 5% significance level will be used for all superiority endpoints, and a one-sided 2.5% significance level will be used for all non-inferiority endpoints.

Safety data (adverse events and serious adverse events as detailed in Section 8) will be presented for all patients by treatment group and comparison, and by relationship to study drug, or underlying colorectal cancer.

Ir vs IrCs comparison

All patients randomised to receive either Ir or IrCs via protocol Version 1.0 or to the Ir vs. IrCs comparison under protocol Version 2.0 (i.e. mutant/unknown *K-RAS* status), regardless of previous anti-EGFR targeted therapy use, will be included in this comparison.

Primary Endpoint

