Kaplan Meier curves for overall survival and progression-free survival will be calculated, and differences between the treatment groups compared using one-sided modified log-rank tests. Survival will also be compared using multivariate modelling, Cox's Proportional Hazards model if appropriate, to adjust for the minimisation factors, previous anti-EGFR targeted therapy use and other important prognostic factors. HRs and corresponding 95% CIs will be presented. Sensitivity analysis will be considered to account for missing data for PFS analysis.

Patients' best response rate⁴² will be assessed by calculating the 95% CI of the difference in response rates between the two treatment groups. In addition, a one-sided chi-squared test for trend (or appropriate version) and logistic regression, to adjust for the minimisation factors,

previous anti-EGFR targeted therapy use and other prognostic factors, will be performed. Sensitivity analyses will be conducted to allow for any deaths from causes other than colorectal cancer, for whom no response status was observed.

Quality of life will be summarised using adjusted for baseline mean scores and 95% CIs for each EORTC QLQ-C30 domain, obtained from a multi-level repeated measures model, assuming missing data at random. Missing data patterns will be examined carefully, and if missing data patterns suggest data are missing not at random, analyses will also be carried out using pattern-mixture models, and data summarised using the Standardised Area Under the Curve. The MRC treatment value/acceptability supplement will be summarised descriptively with bar charts and summary tables for each question. The mean adjusted for baseline total Dermatology Life Quality Index score and scores for each domain will be presented with corresponding 95% confidence intervals.

To assess toxicity, the maximum grade per patient, rate per cycle and all cause mortality within 60 days of randomisation will be summarised descriptively for each treatment group. The difference between the two treatment groups in proportion of patients experiencing grade 3+ diarrhoea within 12 weeks of randomisation will be tested using a two-sided chi-squared test without continuity correction (or appropriate version), and 95% CI's will be presented. Logistic regression will also be used to adjust for the minimisation factors, previous anti-EGFR targeted therapy use and any other prognostic factors. Reasons for stopped treatment will be summarised.

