Kaplan Meier curves for progression-free survival will be calculated, and the difference between the treatment groups compared using a two-sided log-rank test. Survival will also be compared using multivariate modelling, Cox's Proportional Hazards model if appropriate, to adjust for the minimisation factors and other important prognostic factors. HRs and corresponding 95% CIs will be presented. Sensitivity analysis will be considered to account for missing data for PFS analysis.

Patients' best response rate⁴² will be assessed by calculating the 95% CI of the difference in response rates between the two treatment groups. In addition, a two-sided chi-squared test for trend (or appropriate version) and logistic regression, to adjust for the minimisation factors and other prognostic factors will be performed. Sensitivity analyses will be conducted to allow for any deaths from causes other than colorectal cancer.

Quality of life will be summarised using adjusted for baseline mean scores and 95% CIs for each EORTC QLQ-C30 domain, obtained from a multi-level repeated measures model, assuming data to be missing at random. Missing data patterns will be examined carefully, and if missing data patterns suggest data are missing not at random, analyses will also be carried out using pattern-mixture models, and data summarised using the Standardised Area Under the Curve. The MRC treatment value/acceptability supplement will be summarised descriptively with bar charts and summary tables for each question. The mean adjusted for baseline total Dermatology Life Quality Index score and scores for each domain will be presented with corresponding 95% confidence intervals.

To assess toxicity, the maximum grade per patient, rate per cycle and all cause mortality within 60 days of randomisation will be summarised descriptively for each treatment group. Reasons for stopped treatment will be summarised.

It is possible that the presence of skin rash may be associated with the clinical effectiveness of anti-EGFr therapies⁴³. For exploratory purposes it is therefore planned to examine the possibility that the treatment effect, as measured by best response rate, differs according to grade of acneiform rash. Best response rate will be assessed using ordered logistic regression adjusting for treatment, grade of skin toxicity and their interaction.

Ir vs. IrPan comparison (patients with wild-type K-RAS status previously receiving anti-EGFR targeted therapies)

Exploratory Analysis

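### Overall toxicity and 60-day mortality (Ir vs IrCs) and all IrPan toxicity are only described arm by arm, although the stated aims call for a comparison

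*Protocol*

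**What the plan says.** **Aims.** Protocol section 3 (Trial Design) says the trial is designed to show whether IrCs "is non-inferior for anti-cancer efficacy and superior for toxicity compared to" Ir. Under Objective 1, section 2 (Aims and Objectives) says that, once non-inferiority is met, secondary outcomes will determine whether tolerability is improved, and lists the components: "reduced diarrhoea; reduced overall toxicity; improved patient acceptability and/or improved quality of life". Under Objective 2 it says: "Secondary outcome measures will be used to compare the toxicity, patient acceptability and quality of life associated with the two regimens", in patients not previously given anti-EGFR therapy.

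**Endpoints.** For both comparisons, section 10.2 lists nurse-assessed toxicity as maximum grade per patient, rate per cycle and all-cause mortality within 60 days. For Ir vs IrCs it adds that the "toxicity of primary interest is grade 3+ diarrhoea within 12 weeks of randomisation".

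**Analysis.** In section 12, Ir vs IrCs, Secondary Endpoints, the maximum grade, "rate per cycle and all cause mortality within 60 days of randomisation will be summarised descriptively for each treatment group". The same sentence appears under Ir vs IrPan. For Ir vs IrCs only, the proportion "experiencing grade 3+ diarrhoea within 12 weeks of randomisation will be tested using a two-sided chi-squared test without continuity correction", with 95% CIs and an adjusted logistic regression. The general safety paragraph of section 12 adds that safety data "will be presented for all patients by treatment group and comparison, and by relationship to study drug, or underlying colorectal cancer".

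**The concern.** The aims use the language of comparison (superior, determine, compare), but the analysis section prescribes separate summaries for each arm. This is not a detail left open for a statistical analysis plan. The protocol names the method for these endpoints, and in the same section it gives explicit between-arm tests or estimates for treatment failure, response, progression-free status, PFS and OS.

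Two questions depend on the missing estimates:

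- **IrCs.** If it proves non-inferior, the case for using it rests on tolerability. Section 1 reports that ciclosporin raised exposure to irinotecan and its metabolites about 2.3-fold, with a proportionate cut in irinotecan dose, and that systemic side-effects were similar to single-agent irinotecan. It also reports that some patients had ciclosporin reduced or stopped for side-effects. Less diarrhoea therefore does not by itself establish less toxicity overall.
- **IrPan.** Section 1 says no earlier trial had combined panitumumab with single-agent irinotecan, and section 10.4 cites known skin toxicity when justifying OS as the primary endpoint. The randomised difference in harm is what a survival benefit would be weighed against.

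**Working it through.** **1. Reproduce the plan's own toxicity figure.** Inputs from section 11.1: 20% (Ir) vs 10% (IrCs), two-sided 5% chi-squared test without continuity correction, 680 patients before inflation (340 per arm) and 750 after (375 per arm), stated power over 90%.

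Power = Φ{[|p1−p2|·√n − 1.96·√(2·p̄·q̄)] / √(p1q1 + p2q2)}, with p̄ = 0.15, √(2·0.15·0.85) = 0.505 and √(0.16 + 0.09) = 0.5.

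- n = 340: (1.844 − 0.990)/0.5 = 1.708, power 95.6%
- n = 375: (1.936 − 0.990)/0.5 = 1.893, power 97.1%

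The stated figure holds; 266 per arm would already give 90%. The diarrhoea comparison is sound.

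**2. Set aims against planned analyses.**

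| Stated aim | Planned analysis in section 12 | Between-arm estimate? |
|---|---|---|
| IrCs: reduced diarrhoea | chi-squared test, 95% CI, logistic regression | yes |
| IrCs: reduced overall toxicity | maximum grade and rate per cycle, described per arm | no |
| IrCs: 60-day mortality (section 10.2) | described per arm | no |
| IrPan: compare toxicity | maximum grade, rate per cycle and 60-day mortality, described per arm | no, for any toxicity outcome |

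Treatment failure at 12 weeks is tested for Ir vs IrCs. Its definition includes death due to toxicity and irrevocable termination of treatment, so it carries some tolerability information mixed with efficacy.

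**3. What a between-arm estimate would deliver.** Approximate 95% CI half-width = 1.96·√(2p(1−p)/n), with n = 375 per arm (Ir vs IrCs) and 240 per arm (Ir vs IrPan), both from section 11.1. The protocol gives no rate for overall toxicity or 60-day mortality, so p is an assumption shown over a range.

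| Assumed rate p | n = 375 per arm | n = 240 per arm |
|---|---|---|
| 5% | ±3.1 points | ±3.9 points |
| 10% | ±4.3 points | ±5.4 points |
| 20% | ±5.7 points | ±7.2 points |
| 30% | ±6.6 points | ±8.2 points |
| 50% | ±7.2 points | ±9.0 points |

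For example, at p = 30% and n = 375: 1.96·√(0.42/375) = 1.96·0.0335 = 0.066. The lower rates are meant for mortality and the higher ones for any grade 3+ toxicity. The planned sample sizes support usefully precise estimates without change.

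**4. Are the data there?** Section 8.2 collects a named list of toxicities after each cycle, plus any other side-effect of grade 3 or above. Maximum grade per patient is already an endpoint, and deaths are recorded under section 7.9. Both proposed proportions can be formed from planned data.

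**The case against.** The strongest defence is that the core toxicity hypothesis is handled properly. Section 1 gives avoidance of diarrhoea as the reason for IrCs, section 10.2 names it as the toxicity of primary interest, section 11.1 powers it and section 12 tests it. Testing one toxicity and describing the rest is a recognised way to limit multiplicity. This stands for Ir vs IrCs as far as a confirmatory claim goes. It does not extend to overall toxicity, which section 2 lists as a separate component, nor to IrPan, where no toxicity is singled out for testing.

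A reader might infer that the trial can conclude on diarrhoea only, or that the other comparisons are never made. Neither follows. Treatment failure is tested, safety tables are laid out by group and comparison so that arms can be read side by side, and the tolerability list is joined by and/or. What is missing is a stated between-arm estimate.

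A reader might also extend the point to quality of life: "Quality of life will be summarised using adjusted for baseline mean scores and 95% CIs for each EORTC QLQ-C30 domain". The documents do not support that. The means come from a specified multi-level repeated-measures model which already yields the treatment contrast, and which estimate is tabulated is reporting detail.

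Nor can the loss be measured as the power lost by looking for non-overlapping arm intervals. The protocol adopts no such rule, and plans no arm-level intervals for these toxicity outcomes.

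Finally, the mismatch could be removed by rewording the aims. That is true, but it would leave the trial's own question about overall toxicity and IrPan harm without an estimate that it could easily give.

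**Conclusion.** The point holds in limited form. For Ir vs IrCs, overall toxicity and 60-day all-cause mortality have no between-arm estimate despite the aim of showing reduced overall toxicity. For Ir vs IrPan, no toxicity outcome has one despite the aim of comparing toxicity. The descriptive method is written into section 12, so this is a conflict within the protocol and not an omission awaiting the analysis plan.

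The matter is modest. It concerns secondary outcomes and leaves the primary analyses, the sample sizes and the diarrhoea test untouched. The precision figures rest on assumed event rates and on the full planned numbers per arm; a smaller safety population would widen the intervals slightly. The conclusion about the missing estimates does not depend on those assumptions.

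**What to change.** In section 12, under Secondary Endpoints for both Ir vs IrCs and Ir vs IrPan, add the between-arm difference with 95% CI for:

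- the proportion of patients whose maximum toxicity grade (any type) reaches 3 or more within 12 weeks of randomisation, the window already used for diarrhoea;
- all-cause mortality within 60 days of randomisation.

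Label these as secondary and not adjusted for multiplicity, and keep the per-arm tables as supporting description.

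The cost is a few lines of text and four extra unadjusted contrasts (two outcomes in each of two comparisons), to be read with that caution. No new data, visits or patients are needed.

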6.3 Treatment Duration & Treatment Breaks

- The initial treatment period is 12 weeks followed by clinical and radiological re-assessment
- Patients with clinical benefit (radiological and symptomatic response or stabilisation) will be offered further treatment until disease progression or toxicity

- After the initial 12 weeks patients with stable or responding disease may have a planned treatment break of up to 6 weeks (i.e. omit up to 2 cycles of treatment, re-starting up to 9 weeks after the last irinotecan dose). In this event please note:
 - a) there is no change in the scanning schedule i.e. patients should be scanned at 24, 36, 48 weeks etc post randomisation until progression
 - b) patients on IrPan should continue to receive Pan as a single agent during the treatment break (see section 6.2.5)
 - c) If clinical or radiological progression emerges during a break, the patient should resume their allocated treatment, provided that the treating consultant considers this to be in the patient's best interest. Patients on the IrPan arm who have received single-agent Pan during the break should re-start IrPan.

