- If severe skin or nail toxicity occurs, the next panitumumab dose should be withheld and Ir administered alone. Examples of reasons for withholding a planned dose of panitumumab include:
 - Symptomatic skin- or nail-related toxicity requiring strong analgesia, systemic steroids, or felt to be intolerable by the patient

- Skin or nail infection requiring IV antibiotics or IV antifungals
- Need for surgical debridement
- Any skin- or nail-related serious adverse event
- After withholding a dose, panitumumab may be reintroduced at the next treatment cycle, at 75% of the original dose, provided:
 - the adverse event has improved to \leq Grade 2,
 - the subject has recovered to the point where symptomatic skin or nail-related toxicity is no longer felt to be intolerable,
 - systemic steroids or strong analgesics are no longer required,
 - in the case of skin or nail infection, IV antibiotic or IV antifungal treatment is no longer required
- If the 75% dose reduction is tolerated, at the next cycle the panitumumab dose may be escalated to the original dose.
- If, after stopping and resuming panitumumab, a **second** withdrawal is required, any further reintroduction should be at 50% dose. If the 50% dose is tolerated, at the next cycle the panitumumab may be escalated to 75% of the original dose but should not be re-escalated to full dose.
- If, after stopping and resuming panitumumab, a **third** withdrawal is required the patient should be discontinued from receiving panitumumab
- If after withholding a dose of panitumumab, by the next treatment cycle:
 - the adverse event has NOT improved to Grade 2
 - the subject has NOT recovered to the point where symptomatic skin- or nail-related toxicity is no longer felt to be intolerable
 - systemic steroids or strong analgesics are still required
 - or, in the case of skin or nail infection, IV antibiotic or IV antifungal treatment is still required...the patient should be discontinued from receiving panitumumab.
- Panitumumab non-dermatological toxicity
 - In single-agent panitumumab studies, grade 1-2 diarrhoea, nausea, vomiting, abdominal pain and fatigue have been reported. It is therefore possible that panitumumab may contribute to these toxicities when given in combination with irinotecan.
 - Toxicities will be recorded as adverse events on the Treatment Case Report Form (see section 8.2)

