11. STATISTICAL CONSIDERATIONS

11.1 Sample Size

Ir vs IrCs comparison

A non-inferiority design is proposed, based upon the proportion of patients progression-free at 12 weeks from randomisation. In a previous study in a similar patient population receiving irinotecan, median PFS was 4.2 months, with 63.3% of patients progression-free at 12 weeks.³⁸ There are no previous best supportive care (BSC) trials that have included regular CT scan assessments, however in a trial comparing irinotecan with BSC, at the time point that 63% of Ir

patients were alive, less than 40% of BSC patients were alive⁴⁰. On this basis we have estimated that a similar proportion – 40% - of patients on BSC would be expected to be progression-free at 12 weeks applying standard WHO or RECIST criteria. On this basis irinotecan contributes at least 23% to the proportion of patients progression-free at 12 weeks. On the basis of clinician consensus IrCs will be defined as no worse than Ir if median PFS is at least 3 months with IrCs, equivalent to at least 52.7% of patients in the IrCs arm progression-free at 12 weeks. This corresponds to a reduction of no more than 10.6% in the proportion of patients progression-free at 12 weeks which is our non-inferiority margin; retaining more than half the effect that irinotecan has over BSC. The sample size calculation for the Ir vs. IrCs comparison remains the same since there is no data to suggest that *K-RAS* status is a predictive factor for Irinotecan or Ciclosporin.

We will conduct a one-sided test for non-inferiority.³⁹ With 80% power and a significance level of 2.5%, 680 patients are required to test for this degree of non-inferiority using a one-sided chi-squared test without continuity correction. To account for a 10% drop-out or 5% cross-over, 750 patients (375 per arm) would need to be randomised in total. This sample size also gives over 90% power for claiming non-inferiority of PFS using a one-sided modified log-rank test with significance level 2.5% (at least 273 PFS events are required to assess non-inferiority with 80% power), and allows detection of a clinically relevant relative reduction of 50% (from 20% with Ir to 10% with IrCs) in the proportion of patients experiencing grade 3+ diarrhoea within 12 weeks of randomisation, with over 90% power and at a 5% (two-sided) significance level, using a two-sided chi-squared test without continuity correction.

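### Ir versus IrPan has no fixed-window between-arm estimate for diarrhoea, so its maximum-grade summary can reflect longer exposure rather than added toxicity

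*Protocol*

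**What the plan says.** Objective 2 (Protocol section 2) states: "Secondary outcome measures will be used to compare the toxicity, patient acceptability and quality of life associated with the two regimens". Section 6.4 notes that diarrhoea, among other symptoms, was seen with panitumumab alone, and adds: "It is therefore possible that panitumumab may contribute to these toxicities when given in combination with irinotecan".

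For Ir versus IrPan, sections 10.2 and 12 list maximum grade per patient, rate per cycle and 60-day all-cause mortality. Section 12 makes these descriptive ("rate per cycle and all cause mortality within 60 days of randomisation will be summarised descriptively for each treatment group") and adds: "Reasons for stopped treatment will be summarised".

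For Ir versus IrCs the same summaries appear, and section 10.2 goes further: "toxicity of primary interest is grade 3+ diarrhoea within 12 weeks of randomisation". Section 12 says the difference in the proportion with "grade 3+ diarrhoea within 12 weeks of randomisation will be tested using a two-sided chi-squared test without continuity correction", with a 95% CI and a logistic regression adjusted for the minimisation factors and other covariates.

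Sections 6.3 and 7 continue treatment until progression or toxicity. Planned breaks are allowed only after the first 12 weeks, and in them "patients on IrPan should continue to receive Pan as a single agent during the treatment break". Section 8.2 collects toxicity after every cycle until 3 weeks after the last trial drug.

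**The concern.** Maximum grade per patient accumulates: the longer a patient is treated and observed, the more chances there are of a grade 3 event. If panitumumab delays progression, which is the hope behind Objective 2, IrPan patients receive more cycles. Their maximum grade can then look worse even though each cycle is no more toxic.

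Rate per cycle is the natural correction. It is complete only if the risk per cycle stays constant. If risk is concentrated in early cycles, the arm treated longer adds low-risk late cycles to its denominator and looks better.

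With both measures descriptive, a reader could see one leaning against IrPan and the other towards it, with no interval on either. Whether panitumumab adds to irinotecan's main toxicity would then be harder to answer than it need be, although the protocol already contains a measure largely free of both effects.

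**Working it through.** **1. The plan's own figure.** Section 11.1 claims over 90% power for a reduction "from 20% with Ir to 10% with IrCs) in the proportion of patients experiencing grade 3+ diarrhoea within 12 weeks of randomisation", at two-sided 5% with 375 per arm. With z = (|d|√n − 1.96√(2p̄(1−p̄))) / √(p1(1−p1) + p2(1−p2)):

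(0.10 × 19.365 − 1.96 × 0.505) / 0.5 = 1.89, so power is 97%. The claim is confirmed.

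**2. Inputs for the exposure illustration.**
- From section 11.1: median PFS on Ir 4.2 months; grade 3+ diarrhoea 20% over 12 weeks on Ir.
- From section 6.2: 3-week cycles (0.69 months), so four cycles in 12 weeks.
- Assumed: treatment lasts exactly as long as PFS; PFS is exponential; the PFS hazard ratio is 0.7 (borrowed from the OS target in section 11.1), 0.8 or 1.0; the risk per cycle is the same in both arms (no true panitumumab effect); risk after cycle 4 is unchanged, halved, quartered or zero. The protocol gives no PFS target for IrPan and no time pattern for diarrhoea.

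**3. Formulas.**
- Risk per cycle: p = 1 − 0.8^(1/4) = 0.0543.
- Chance of remaining on treatment from one cycle to the next: s = exp(−ln2 × 0.69/median). For Ir, s = 0.892. For IrPan at HR 0.7 (median 4.2/0.7 = 6.0 months), s = 0.923.
- Mean cycles, 1/(1−s): 9.3 for Ir and 13.1 for IrPan.
- With q = (1−p)s, ever grade 3+ under constant risk is p/(1−q): 0.0543/0.156 = 34.8% for Ir and 0.0543/0.127 = 42.8% for IrPan.
- Within four cycles, p(1−q⁴)/(1−q): 17.1% and 17.9%.
- Rate per cycle when later risk is multiplied by r: p[1 − (1−r)s⁴].

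**4. Results at HR 0.7, with no true difference in risk (Ir v IrPan).**

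| Risk after cycle 4 | Ever grade 3+ | Excess (points) | Rate per cycle | Within 12 weeks |
|---|---|---|---|---|
| Unchanged | 34.8% v 42.8% | 8.0 | 5.43% v 5.43% | 17.1% v 17.9% |
| Halved | 27.6% v 33.4% | 5.8 | 3.71% v 3.45% | 17.1% v 17.9% |
| Quartered | 22.9% v 26.8% | 3.9 | 2.85% v 2.47% | 17.1% v 17.9% |
| Zero | 17.1% v 17.9% | 0.8 | 1.99% v 1.48% | 17.1% v 17.9% |

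At HR 0.8 the excess is 4.9 points with unchanged risk (34.8% v 39.7%) and 0.5 with zero late risk (17.1% v 17.6%). At HR 1.0 it is nil. A continuous-time version gives much the same at HR 0.7: 32.9% v 41.2% with constant hazard, and 16.2% v 17.2% within 12 weeks.

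**5. Rate per cycle when there is a true effect.** Let panitumumab raise the risk per cycle by a factor of 1.25, with HR 0.7. Under constant risk the rate shows it correctly: 6.78/5.43 = 1.25. If later risk halves, it shows 4.32/3.71 = 1.16. If later risk quarters, it shows 3.08/2.85 = 1.08. The 12-week proportions are 17.1% v 22.0% throughout.

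**6. Precision of the 12-week measure for IrPan.** With 240 per arm and 20% in each, the half-width is 1.96 × √(2 × 0.2 × 0.8/240) = 7.2 points. Power by the formula in step 1 is 72% for 20% v 30% and 85% for 20% v 32%. These IrPan rates are assumptions.

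**The case against.** Several points on the other side stand.

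- A reader might infer that IrPan toxicity is judged only on maximum grade and rate per cycle. It is not. Mortality within 60 days is a fixed-window measure, reasons for stopping are summarised, and section 12 also tabulates adverse and serious adverse events by treatment group and comparison. None of these, however, is specified as a fixed-window between-arm estimate for diarrhoea.
- A reader might infer that both main measures are distorted by unequal exposure. Rate per cycle is itself an exposure adjustment and is exact under constant risk. Its drift needs falling risk, which is plausible because section 6.4 reduces the irinotecan dose after severe diarrhoea, but the protocol gives no figures on it.
- A reader might infer that panitumumab-only infusions in breaks dilute the IrPan rate. That requires counting them as cycles. Section 6.1 identifies day 1 of a cycle with irinotecan administration, and section 6.3 describes a break as omitting cycles, so the text leans the other way.
- The asymmetry has a reason. Reduced toxicity is the purpose of Objective 1, whereas Objective 2 is mainly about efficacy. The background table shows grade 3 diarrhoea in only 1% on panitumumab alone. This explains the emphasis, but Objective 2 still promises a toxicity comparison.
- A higher maximum grade through longer treatment is a real burden on patients. It answers a legitimate but different question.
- The SAP is not shown and may set a window. The DMEC reviewed first-cycle toxicity in the first 100 patients (section 12.1), an exposure-matched look, though as monitoring rather than a reported endpoint.

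**Conclusion.** The point holds as a modest weakness in the analysis fixed by sections 10.2 and 12. The maximum-grade summary for Ir versus IrPan can show an excess due to longer treatment alone: about 0 to 8 points for assumed PFS hazard ratios of 1.0 to 0.7 and late risk from zero to unchanged, against about 1 point or less within 12 weeks. The size rests on borrowing the OS hazard ratio for PFS, equating treatment time with PFS, and an assumed time pattern of risk.

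It would go too far to conclude that panitumumab's effect on diarrhoea will be misreported. The existing summaries can be misread, but they are shown side by side, can lean in opposite directions, and come from per-cycle data that also allow a 12-week figure. The documents contain no contradiction or wrong number here.

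**What to change.** In sections 10.2 and 12, add to Ir versus IrPan (wild-type, not pre-treated) the proportion with grade 3+ diarrhoea within 12 weeks of randomisation, with the difference between arms, its 95% CI, and logistic regression adjusted for the minimisation factors. Present it as a secondary safety estimate beside the existing summaries, which should stay.

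As a minor clarification, state that panitumumab-only infusions are tabulated separately from irinotecan cycles when rate per cycle is reported.

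This changes analysis wording only. Case report forms already record toxicity after each cycle in both arms, and no dose, schedule or sample size is affected. The cost is one more secondary comparison, with limited power for small differences (26% for 20% v 25%), so the interval should carry the interpretation.
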